11.1.3 Guidelines for Evaluation of Measurable Disease

All measurements should be taken and recorded in metric notation using a ruler or calipers. All baseline evaluations should be performed as closely as possible to the beginning of treatment and never more than 4 weeks before the beginning of the treatment.

The same method of assessment and the same technique should be used to characterize each identified and reported lesion at baseline and during follow-up. Imaging-based evaluation is preferred to evaluation by clinical examination unless the lesion(s) being followed cannot be imaged but are assessable by clinical exam.

Clinical lesions: Clinical lesions will only be considered measurable when they are superficial (e.g., skin nodules and palpable lymph nodes) and ≥ 10 mm diameter as assessed using calipers (e.g., skin nodules). In the case of skin lesions, documentation by color photography, including a ruler to estimate the size of the lesion, is recommended.

Chest x-ray: Lesions on chest x-ray are acceptable as measurable lesions when they are clearly defined and surrounded by aerated lung. However, CT is preferable.

Conventional CT and MRI: This guideline has defined measurability of lesions on CT scan based on the assumption that CT slice thickness is 5 mm or less. If CT scans have slice thickness greater than 5 mm, the minimum size for a measurable lesion should be twice the slice thickness. MRI is also acceptable in certain situations (e.g., for body scans).

As with CT, if an MRI is performed, the technical specifications of the scanning sequences used should be optimized for the evaluation of the type and site of disease. Furthermore, as with CT, the modality used at follow-up should be the same as was used at baseline and the lesions should be measured/assessed on the same pulse sequence. It is beyond the scope of the RECIST guidelines to prescribe specific MRI pulse sequence parameters for all scanners, body parts, and diseases. Ideally, the same type of scanner should be used and the image acquisition protocol should be followed as closely as possible to prior scans. Body scans should be performed with breath-hold scanning techniques, if possible.

PET-CT: At present, the low dose or attenuation correction CT portion of a combined PET-CT is not always of optimal diagnostic CT quality for use with RECIST measurements. However, if the site can document that the CT performed as part of a PET-CT is of identical diagnostic quality to a diagnostic CT (with IV and oral contrast), then the CT portion of the PET-CT can be used for RECIST measurements and can be used interchangeably with conventional CT in accurately measuring cancer lesions over time. Note, however, that the PET portion of the CT introduces additional data which may bias an investigator if it is not routinely or serially performed.

Ultrasound: Ultrasound is not useful in assessment of lesion size and should not be used as a method of measurement. Ultrasound examinations cannot be reproduced in their entirety for independent review at a later date and, because they are operator dependent, it cannot be guaranteed that the same technique and measurements will be taken from one assessment to the next. If new lesions are identified by ultrasound in the course of the study, confirmation by CT or MRI is advised. If there is concern about radiation exposure at CT, MRI may be used instead of CT in selected instances.

Endoscopy, Laparoscopy: The utilization of these techniques for objective tumor evaluation is not advised. However, such techniques may be useful to confirm complete pathological response when biopsies are obtained or to determine relapse in trials where recurrence following complete response (CR) or surgical resection is an endpoint.

Tumor markers: Tumor markers alone cannot be used to assess response. If markers are initially above the upper normal limit, they must normalize for a patient to be considered in complete clinical response. Specific guidelines for both CA-125 response (in recurrent ovarian cancer) and PSA response (in recurrent prostate cancer) have been published [*JNCI* 96:487-488, 2004; *J Clin Oncol* 17, 3461-3467, 1999; *J Clin Oncol* 26:1148-1159, 2008]. In addition, the Gynecologic Cancer Intergroup has developed CA-125 progression criteria which are to be integrated with objective tumor assessment for use in first-line trials in ovarian cancer [*JNCI* 92:1534-1535, 2000].

Cytology, Histology: These techniques can be used to differentiate between partial responses (PR) and complete responses (CR) in rare cases (e.g., residual lesions in tumor types, such as germ cell tumors, where known residual benign tumors can remain).

The cytological confirmation of the neoplastic origin of any effusion that appears or worsens during treatment when the measurable tumor has met criteria for response or stable disease is mandatory to differentiate between response or stable disease (an effusion may be a side effect of the treatment) and progressive disease.

FDG-PET: While FDG-PET response assessments need additional study, it is sometimes reasonable to incorporate the use of FDG-PET scanning to complement CT scanning in assessment of progression (particularly possible 'new' disease). New lesions on the basis of FDG-PET imaging can be identified according to the following algorithm:

- a. Negative FDG-PET at baseline, with a positive FDG-PET at follow-up is a sign of PD based on a new lesion.
- b. No FDG-PET at baseline and a positive FDG-PET at follow-up: If the positive FDG-PET at follow-up corresponds to a new site of disease confirmed by CT, this is PD. If the positive FDG-PET at follow-up is not confirmed as a new site of disease on CT, additional follow-up CT scans are needed to determine if there is truly progression occurring at that site (if so, the date of PD will be the date of the initial abnormal FDG-PET scan). If the positive FDG-PET at follow-up corresponds to a pre-existing site of disease on CT that is not progressing on the basis of the anatomic images, this is not PD.
- c. FDG-PET may be used to upgrade a response to a CR in a manner similar to a biopsy in cases where a residual radiographic abnormality is thought to represent fibrosis or scarring. The use of FDG-PET in this circumstance should be prospectively described in the protocol and supported by disease-specific medical literature for the indication. However, it must be acknowledged that both approaches may lead to false positive CR due to limitations of FDG-PET and biopsy resolution/sensitivity.

Note: A ‘positive’ FDG-PET scan lesion means one which is FDG avid with an uptake greater than twice that of the surrounding tissue on the attenuation corrected image.

11.1.4 Response Criteria

11.1.4.1 Evaluation of Target Lesions

Complete Response (CR): Disappearance of all target lesions. Any pathological lymph nodes (whether target or non-target) must have reduction in short axis to <10 mm.

Partial Response (PR): At least a 30% decrease in the sum of the diameters of target lesions, taking as reference the baseline sum diameters.

Progressive Disease (PD): At least a 20% increase in the sum of the diameters of target lesions, taking as reference the smallest sum on study (this includes the baseline sum if that is the smallest on study). In addition to the relative increase of 20%, the sum must also demonstrate an absolute increase of at least 5 mm. (Note: the appearance of one or more new lesions is also considered progressions).

Stable Disease (SD): Neither sufficient shrinkage to qualify for PR nor sufficient increase to qualify for PD, taking as reference the smallest sum diameters while on study.

11.1.4.2 Evaluation of Non-Target Lesions

Complete Response (CR): Disappearance of all non-target lesions and normalization of tumor marker level. All lymph nodes must be non-pathological in size (<10 mm short axis).

Note: If tumor markers are initially above the upper normal limit, they must normalize for a patient to be considered in complete clinical response.

Non-CR/Non-PD: Persistence of one or more non-target lesion(s) and/or maintenance of tumor marker level above the normal limits.

Progressive Disease (PD): Appearance of one or more new lesions and/or *unequivocal progression* of existing non-target lesions. *Unequivocal progression* should not normally trump target lesion status. It must be representative of overall disease status change, not a single lesion increase.

Although a clear progression of “non-target” lesions only is exceptional, the opinion of the treating physician should prevail in such circumstances, and the progression status should be confirmed at a later time by the review panel (or Principal Investigator).

11.1.4.3 Evaluation of Best Overall Response

The best overall response is the best response recorded from the start of the treatment until disease progression/recurrence (taking as reference for progressive disease the smallest measurements recorded since the treatment started). The patient's best response assignment will depend on the achievement of both measurement and confirmation criteria.

For Patients with Measurable Disease (i.e., Target Disease)

Target Lesions	Non-Target Lesions	New Lesions	Overall Response	Best Overall Response when Confirmation is Required*
CR	CR	No	CR	≥4 wks. Confirmation**
CR	Non-CR/Non-PD	No	PR	
CR	Not evaluated	No	PR	
PR	Non-CR/Non-PD/not evaluated	No	PR	≥4 wks. Confirmation**
SD	Non-CR/Non-PD/not evaluated	No	SD	Documented at least once ≥4 wks. from baseline**
PD	Any	Yes or No	PD	
Any	PD***	Yes or No	PD	
Any	Any	Yes	PD	no prior SD, PR or CR

* See RECIST 1.1 manuscript for further details on what is evidence of a new lesion.
 ** Only for non-randomized trials with response as primary endpoint.
 *** In exceptional circumstances, unequivocal progression in non-target lesions may be accepted as disease progression.

Note: Patients with a global deterioration of health status requiring discontinuation of treatment without objective evidence of disease progression at that time should be reported as “*symptomatic deterioration*.” Every effort should be made to document the objective progression even after discontinuation of treatment.

For Patients with Non-Measurable Disease (i.e., Non-Target Disease)

Non-Target Lesions	New Lesions	Overall Response
CR	No	CR
Non-CR/non-PD	No	Non-CR/non-PD*
Not all evaluated	No	not evaluated
Unequivocal PD	Yes or No	PD
Any	Yes	PD

* 'Non-CR/non-PD' is preferred over 'stable disease' for non-target disease since SD is increasingly used as an endpoint for assessment of efficacy in some trials so to assign this category when no lesions can be measured is not advised

11.1.5 Duration of Response

Duration of overall response: The duration of overall response is measured from the time measurement criteria are met for CR or PR (whichever is first recorded) until the first date that recurrent or progressive disease is objectively documented (taking as reference for progressive disease the smallest measurements recorded since the treatment started).

The duration of overall CR is measured from the time measurement criteria are first met for CR until the first date that progressive disease is objectively documented.

Duration of stable disease: Stable disease is measured from the start of the treatment until the criteria for progression are met, taking as reference the smallest measurements recorded since the treatment started, including the baseline measurements.

12. DATA REPORTING / REGULATORY REQUIREMENTS

Adverse event lists, guidelines, and instructions for AE reporting can be found in [Section 7.0](#) (Adverse Events: List and Reporting Requirements).

12.1 Data Reporting

12.1.1 Method

This study will be monitored by the Clinical Trials Monitoring Service (CTMS). Data will be collected in the Center for Cancer Research C3D database and will be transmitted to CTMS electronically at least once every 2 weeks.

Note: All adverse events that have occurred on the study, including those reported through CTEP-AERS, must be reported via the monitoring method identified above.

12.1.2 Responsibility for Data Submission

N/A

12.2 CTEP Multicenter Guideline

N/A

12.3 Collaborative Agreements Language

The agent(s) supplied by CTEP, DCTD, NCI used in this protocol is/are provided to the NCI under a Collaborative Agreement (CRADA, CTA, CSA) between the Pharmaceutical

Company(ies) (hereinafter referred to as "Collaborator(s)") and the NCI Division of Cancer Treatment and Diagnosis. Therefore, the following obligations/guidelines, in addition to the provisions in the "Intellectual Property Option to Collaborator" (http://ctep.cancer.gov/industryCollaborations2/intellectual_property.htm) contained within the terms of award, apply to the use of the Agent(s) in this study:

1. Agent(s) may not be used for any purpose outside the scope of this protocol, nor can Agent(s) be transferred or licensed to any party not participating in the clinical study. Collaborator(s) data for Agent(s) are confidential and proprietary to Collaborator(s) and shall be maintained as such by the investigators. The protocol documents for studies utilizing Agents contain confidential information and should not be shared or distributed without the permission of the NCI. If a copy of this protocol is requested by a patient or patient's family member participating on the study, the individual should sign a confidentiality agreement. A suitable model agreement can be downloaded from: <http://ctep.cancer.gov>.
2. For a clinical protocol where there is an investigational Agent used in combination with (an)other Agent(s), each the subject of different Collaborative Agreements, the access to and use of data by each Collaborator shall be as follows (data pertaining to such combination use shall hereinafter be referred to as "Multi-Party Data"):
 - a. NCI will provide all Collaborators with prior written notice regarding the existence and nature of any agreements governing their collaboration with NCI, the design of the proposed combination protocol, and the existence of any obligations that would tend to restrict NCI's participation in the proposed combination protocol.
 - b. Each Collaborator shall agree to permit use of the Multi-Party Data from the clinical trial by any other Collaborator solely to the extent necessary to allow said other collaborator to develop, obtain regulatory approval or commercialize its own Agent.
 - c. Any Collaborator having the right to use the Multi-Party Data from these trials must agree in writing prior to the commencement of the trials that it will use the Multi-Party Data solely for development, regulatory approval, and commercialization of its own Agent.
3. Clinical Trial Data and Results and Raw Data developed under a Collaborative Agreement will be made available to Collaborator(s), the NCI, and the FDA, as appropriate and unless additional disclosure is required by law or court order as described in the IP Option to Collaborator (http://ctep.cancer.gov/industryCollaborations2/intellectual_property.htm). Additionally, all Clinical Data and Results and Raw Data will be collected, used, and disclosed consistent with all applicable federal statutes and regulations for the protection of human subjects, including, if applicable, the Standards for Privacy of Individually Identifiable Health Information set forth in 45 C.F.R. Part 164.
4. When a Collaborator wishes to initiate a data request, the request should first be sent to the NCI, who will then notify the appropriate investigators (Group Chair for Cooperative Group studies, or PI for other studies) of Collaborator's wish to contact them.

5. Any data provided to Collaborator(s) for Phase 3 studies must be in accordance with the guidelines and policies of the responsible Data Monitoring Committee (DMC), if there is a DMC for this clinical trial.
6. Any manuscripts reporting the results of this clinical trial must be provided to CTEP by the Group office for Cooperative Group studies or by the principal investigator for non-Cooperative Group studies for immediate delivery to Collaborator(s) for advisory review and comment prior to submission for publication. Collaborator(s) will have 30 days from the date of receipt for review. Collaborator shall have the right to request that publication be delayed for up to an additional 30 days to ensure that Collaborator's confidential and proprietary data, in addition to Collaborator(s)'s intellectual property rights, are protected. Copies of abstracts must be provided to CTEP for forwarding to Collaborator(s) for courtesy review as soon as possible and preferably at least three (3) days prior to submission, but in any case, prior to presentation at the meeting or publication in the proceedings. Press releases and other media presentations must also be forwarded to CTEP prior to release. Copies of any manuscript, abstract and/or press release/ media presentation should be sent to: E-mail: [contact]

The Regulatory Affairs Branch will then distribute them to Collaborator(s). No publication, manuscript or other form of public disclosure shall contain any of Collaborator's confidential/ proprietary information.

12.4 Genomic Data Sharing Plan

The NIH Genomic Data Sharing (GDS) Policy does not apply to this protocol as we will be performing exploratory genetic analysis of no more than 80 patient samples; therefore, this study does not meet GDS criteria, and a GDS plan is not warranted.

13. STATISTICAL CONSIDERATIONS

13.1 Study Design

The Phase I portion of the study will use a standard 3+ 3 design without intra-patient dose escalation. The MTD or recommended Phase II dose is the dose level at which no more than 1 of 6 patients experience DLT during the first cycle of treatment, and the dose below that at which at least 2 (of \leq 6) patients have DLT as a result of the drug.

The Phase II portion will follow the Simon two-stage minimax design and will consist of three separately evaluated cohorts: patients with NSCLC, colon, and granulosa cell ovarian cancer. For NSCLC and colon, the maximum cohort size would be set at 25 evaluable patients. If at least 5 responses (at least 20%) are observed among the 25 evaluable patients, this regimen would be considered worthy of further testing in this disease. If no more than 1 response (no more than 6%) is observed among the initial 16 patients, the cohort would be terminated early and declared negative. This design yields at least 90% power to detect a true response rate of at

least 30%. It yields at least .90 probability of a negative result if the true response rate is no more than 10%, with at least .52 probability of early negative stopping. For granulosa cell ovarian cancer, maximum cohort size would be set at 15 evaluable patients. If at least 4 responses (at least 27%) are observed among the 15 evaluable patients, this regimen would be considered worthy of further testing in this disease. If no responses are observed among the initial 8 patients, the cohort would be terminated early and declared negative. This design yields at least 90% power to detect a true response rate of at least 40%. It yields at least .945 probability of a negative result if the true response rate is no more than 10%, with at least .43 probability of early negative stopping.

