13.2 Sample Size/Accrual Rate

The Phase I portion of the study is designed to have 8 dose escalation cohorts, with a standard design using 3 patients per cohort, unless DLT is noted, in which point up to 6 patients may be enrolled in a cohort. In addition, up to an additional 15 patients will be enrolled at the MTD to further define the dose and evaluate PD studies at this dose level; with that number, and a tumor biopsy QA criteria failure rate of 50% with respect to paired (pre- and post-dose) biopsies, we have an 85% likelihood of having at least 6 usable PD samples, and 95% likelihood of having at least 5 usable samples. Biopsy tissue quality will be monitored and accrual will stop once we have obtained 6 usable paired samples. To allow for a small number of patients who may not be evaluable, the accrual ceiling for this trial is set at 65 (55 patients plus 10 healthy volunteers).

The Phase II portion of the study is designed to have up to 65 evaluable patients, and to allow for a small number of patients who may not be evaluable, the accrual ceiling for the Phase II portion is set at 75 patients. It is anticipated that 2-3 patients per month may be enrolled onto this study. Depending on whether the Phase I expansion and Phase II cohorts accrue to completion, it is expected that approximately 4 years will be required to accrue the number of patients necessary to complete the entire trial.

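### Do the .52 early-stopping probability and the 95% biopsy yield in Section 13 overstate what the design gives?

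*Combined protocol and SAP*

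**What the plan says.** Section 13.1 sets out a Simon two-stage minimax design, applied separately to the NSCLC and colon cohorts. "For NSCLC and colon, the maximum cohort size would be set at 25 evaluable patients". "If no more than 1 response (no more than 6%) is observed among the initial 16 patients", the cohort closes and is declared negative. "If at least 5 responses (at least 20%) are observed among the 25 evaluable patients", the regimen is judged worth further testing. The section then lists operating characteristics, each worded as a minimum: power of 90% at a 30% response rate, a negative-result probability of .90 at response rates up to 10%, and, for the same rates, "with at least .52 probability of early negative stopping".

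The granulosa cell cohort has its own rule: stop after 0 responses in 8, and succeed with 4 or more in 15. It has a parallel list, in which the early-stopping entry reads "with at least .43 probability of early negative stopping".

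Section 13.2 justifies the Phase I expansion of up to 15 patients by biopsy yield. Assuming half of the paired biopsies fail quality criteria, it says "we have an 85% likelihood of having at least 6 usable PD samples" and a "95% likelihood of having at least 5 usable samples". Accrual to the expansion ends once 6 usable pairs are in hand.

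**The concern.** A reader who recomputes Section 13 finds two probabilities that do not come out, and in both cases the printed figure is the more favourable one. The early-stopping figure is the sharper case because it is worded as a guaranteed minimum over all response rates up to 10%, and a minimum must hold at the boundary.

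The probability of early termination tells a reviewer how often an inactive regimen is dropped at 16 patients instead of going on to 25, and here it covers two of the three Phase II cohorts. A wrong value could also mean that the printed stopping rule is not the one that was designed: a stage size or cut-off mistyped in the text, with the probability carried over from the intended design. Power and the false-positive rate would then be in doubt too. That possibility is the reason to check.

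**Working it through.** **Inputs.** NSCLC and colon: n1 = 16, stop at 1 response or fewer; n = 25, success at 5 or more; null rate 10%, target rate 30% (Section 13.1). Granulosa cell: n1 = 8, stop at 0; n = 15, success at 4 or more; rates 10% and 40% (Section 13.1). Biopsies: 15 patients, 50% paired failure rate (Section 13.2). All calculations are exact binomial.

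**1. Early stopping, NSCLC and colon.** At a 10% response rate:

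P(X ≤ 1 | 16, 0.10) = 0.9^16 + 16 × 0.1 × 0.9^15 = 0.1853 + 0.3294 = 0.5147.

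The probability falls as the response rate rises, so 0.5147 is the minimum over rates up to 10%. The stated figure is .52, a shortfall of 0.0053. At a rate of 9.9% the same formula gives 0.5202, so the printed bound fails only between about 9.9% and 10%.

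**2. Is the printed rule the intended one?** Changing the first-stage size does not give .52: n1 = 15 gives 0.549 and n1 = 17 gives 0.482. A search over two-stage designs for 10% versus 30%, with both error rates capped at 10%, returns n1 = 16, stop at 1, n = 25, success at 5 as the minimax design. The rule is right; only the printed probability is off.

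**3. Error rates of that design.** Sum over first-stage counts that continue, with 9 patients in stage two.

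| Stage 1 responses | Probability at 10% | Reaches 5 or more | Product |
|---|---|---|---|
| 2 | 0.2745 | 0.0530 | 0.0145 |
| 3 | 0.1423 | 0.2252 | 0.0320 |
| 4 | 0.0514 | 0.6126 | 0.0315 |
| 5 or more | 0.0170 | 1 | 0.0170 |

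The unrounded total is 0.0951, so the negative-result probability is 1 − 0.0951 = 0.9049 (stated: at least .90). At 30% the same sum is 0.0393 + 0.1178 + 0.1958 + 0.5501 = 0.9030 (stated: at least 90%). Both hold.

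**4. Granulosa cell cohort.** Early stopping is 0.9^8 = 0.4305 (stated .43). At 10%, the chance of success is 0.0098 + 0.0223 + 0.0173 + 0.0050 = 0.0544, so the negative-result probability is 0.9456 (stated .945). At 40%, power is 0.0520 + 0.1759 + 0.2709 + 0.4059, which is 0.9046 before rounding the terms (stated 90%). All three hold.

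**5. Biopsy yield.** There are 2^15 = 32768 equally likely outcomes.

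- At least 6 usable: 1 − (1 + 15 + 105 + 455 + 1365 + 3003)/32768 = 1 − 4944/32768 = 84.9% (stated 85%).
- At least 5 usable: 1 − 1941/32768 = 94.1% (stated 95%).

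Neighbouring cohort sizes do not give 95% either: 14 patients give 91.0% and 16 give 96.2%. A failure rate of 48.9% in place of 50% does.

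**6. What the slip is worth.** Expected enrolment per cohort at a 10% response rate is 16 + 9 × (1 − 0.5147) = 20.37. With the printed figure it would be 16 + 9 × 0.48 = 20.32. The difference is about 0.05 of a patient.

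**The case for a change.** The best argument for a correction is that the early-stopping statement is false as written and nothing rescues it. The value 0.5147 becomes .51 whether rounded or truncated. The other minima in the paragraph are true floors; 0.9456, for instance, is given as .945 and not rounded up. A standard property of the design is misquoted for two cohorts, could be copied into a results report, and would take a two-character edit to put right.

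The factual part stands: .52 is a slip. The step to changing the plan does not follow. No stopping boundary, sample size, power or error rate is derived from that number, and the rule that investigators apply is the correct minimax rule. The suggestion of a favourable lean is weak, because .90, .945 and .43 are all printed below their exact values.

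The biopsy half of the argument is weaker. Neither percentage in Section 13.2 is worded as a minimum, and rounding to the nearest 5 points turns 84.9 into 85 and 94.1 into 95. The plan does not state that convention, but it accounts for both figures. The 50% failure rate is itself a round guess, and 1.1 points on that guess closes the gap. Sections 5 and 9.2.3.2 also provide for replacing patients without paired biopsies, and 9.2.3.2 for repeating a failed attempt, so 15 independent single tries only approximates what would happen. In fairness, Section 13.2 ties its percentages to the 15 patients, so the simple binomial is the calculation its authors meant. Even so, the accrual target is 6 pairs, and the figure for 6 is right.

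**Conclusion.** No change to the plan follows. The early-stopping figure in Section 13.1 is a clerical slip of 0.0053: the exact minimum is 0.5147, which supports .51 and not .52. The biopsy figure in Section 13.2 is 0.9 percentage points above the exact 94.1%, is compatible with coarse rounding, and does not amount to an error in an estimate built on an assumed 50% failure rate.

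The possibility that mattered, a misprinted stopping rule, is ruled out. The printed rule is the minimax design for 10% versus 30%, and the power and negative-result probability that support a conclusion in each cohort are met: 0.903 and 0.905 for NSCLC and colon, 0.905 and 0.946 for granulosa cell. Amending the text would alter nothing that the trial does or can conclude. Anyone who reports the design can quote the exact value directly.

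This rests on independent patients with a common response rate within each cohort, the interim look falling at exactly 16 (or 8) evaluable patients, and the stopping rules being followed as written.
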